9.1.1.4 Lack of Compliance

The investigator may stop the study drug and withdraw the subject if in their opinion the subject is not complying with study procedures, including, but not limited to, dosing of the study drug.

9.1.2 Study Termination

- The study can be stopped at any time if deemed necessary by the Sponsor Medical Monitor, in consultation with the Study Medical Monitor, due to safety concerns. Safety will be monitored on an ongoing basis via periodic masked review of AEs and other safety endpoints.
 - If it is observed that visual acuity worsens by 2 lines (Base LogMAR change of 0.2 using ETDRS chart) at Visit 6 (POD22) in the treated study eye as compared to Visit 2 (POD1), in 6 consecutive subjects, no further doses of study drug will be administered to any subjects in the study until a

comprehensive evaluation can be performed, and, if possible, a cause is identified.

- Safety assessments will be performed throughout the course of the study. The APP13007 Investigator's Brochure, Section 1.4.1 and the Risk Mitigation plan in Table 2 provide guidance for the Investigator on potential anticipated AEs that may occur. Any potential important safety issues that arise will be reviewed by the Study Medical Monitor, in consultation with the Sponsor Medical Monitor, to identify the appropriate course of action.
- If the Sponsor elects to terminate the study for any reason, the Investigator will be responsible for notification of the IRB and will withhold further dosing of study drug.

9.2 DOSE MODIFICATION

No dose modification is permitted.

All instances of missed doses must be recorded.

Note: Study drug bottle will be replaced as soon as possible if a bottle is lost or otherwise compromised before Visit 5 (POD15) (see [Section 5.1.2](#)). This may require an unscheduled visit.

9.3 DOSING INTERRUPTIONS

Investigator is not allowed to modify the dosing regimen due to an AE or any other circumstance, but the Investigator has the option of stopping study drug after consultation with the Study Medical Monitor, if feasible.

Subjects will be permitted to restart study drug if there is a temporary dosing interruption of study drug of not more than 1 day due to an AE.

9.4 RESCUE MANAGEMENT

9.4.1 Criteria for Starting Rescue Medication

Any subject not responding to the study drug because of lack of efficacy at any time after randomization at Visit 2 (POD1) may be rescued and placed on an appropriate alternative therapy determined by the Investigator.

In general, at any visit, a subject with worsening inflammation or showing no improvement in degree of inflammation compared with the previous visit is eligible for rescue therapy at the

discretion of the Investigator. However, the following guidance is provided to Investigators for consistency in the way subjects are rescued:

1. Subjects who, on examination of the anterior chamber, have one or more of the following quantitative criteria should be rescued and discontinued from study drug dosing and placed on rescue mediation:
 - An increase of ACC count by > 15 cells from the Visit 2 (POD1) pre-dose baseline.
 - A ≥ 2 grade increase in ACF grade from the Visit 2 (POD1) pre-dose baseline.
2. Subjects who have the following qualitative criteria may be rescued. If the subject is rescued, the study drug should be discontinued and rescue medication started:
 - Subjects who have pain and/or photophobia that does not improve, even when there is an improvement in ACC count and/or ACF grade, may be rescued at the discretion of the investigator.
 - Subjects who have pain and/or photophobia that worsens may be rescued at the discretion of the investigator.

Initiation of rescue medication is at the discretion of the Investigator. However, it is recommended that the Investigator uses the above guidance to determine when to rescue a subject. If the quantitative ACC count or ACF grade criteria are not met, the Investigator should discuss the qualitative reason(s) for rescue with the Study Medical Monitor for consistency across the study.

9.4.2 Management

Investigators will use clinical judgment to determine when to rescue a subject using the guidance provided in [Section 9.4.1](#) and the appropriate rescue medication to use. Rescued subjects will stop study drug and will continue in the study, and will be assessed at each subsequent visit, if possible, through completion of the Visit 6 (POD22) assessments (if participating in the Main study) or Visit 7 (POD85) assessments (if participating in the Endothelial Cell Sub-study) (Table 1) or until the Investigator has deemed the subject is stable and can be released from the study.

If a subject needs to be rescued at Visit 5 (POD15), the Visit 5 (POD15) assessments (Table 1) should be completed before the subject is administered rescue medication.

Rescued subjects will be considered treatment failures, and the need for rescue medication will not be considered as an AE.

An AE occurring at the time of rescue will be recorded in the eCRF and will be followed by the Investigator to stabilization or resolution of the AE or the end of the study (whichever comes last).

If a subject is rescued, this event will be recorded in the eCRF (not as an AE). Medications used for rescue will be recorded in the ConMeds section of the eCRF, indicating that they were used for rescue.

9.5 MANAGEMENT OF INCREASED IOP

9.5.1 Criteria for Starting IOP-Lowering Medication

Investigators should use the following criteria to determine whether to start IOP-lowering medication:

- After randomization, an IOP > 30 mmHg in the study eye
- After randomization, an IOP ≥ 21 mmHg **AND** an increase of > 10 mmHg from the Visit 2 (POD1) pre-dose baseline in the study eye (both of these criteria must be met)

Initiation of IOP-lowering medication is at the discretion of the Investigator even if neither of the above criteria are met, however, it is recommended that the Investigator uses these criteria to determine when to consider a subject for IOP-lowering medication.

9.5.2 Management

Investigator will use clinical judgment to determine the appropriate IOP-lowering medication to use and when to withdraw study drug and procedures, in consultation with the Study Medical Monitor.

It is important to note that prostaglandin-based IOP lowering medications are prohibited in this study.

- After randomization and start of study drug, if a subject has an IOP > 30 mmHg the Investigator may commence non-prostaglandin-based IOP-lowering medication while continuing the study drug, with appropriate follow-up at the next planned visit or at an unscheduled visit. The subject may require assessment at an unscheduled visit at the investigator's discretion.
 - If the IOP is < 30 mmHg at the next visit, the subject may continue on study drug.
 - If at the next visit, the IOP remains > 30 mmHg while on IOP-lowering medication, then the study drug may be discontinued and alternative IOP-lowering medication

may be started, after consultation with the Study Medical Monitor. The subject should continue in the study and complete the assessments indicated in Table 1 through Visit 6 (POD22) (Main Study) or Visit 7 (POD85) (Endothelial Cell Sub-study). The Study Medical Monitor should discuss the persistent elevation of IOP with the Sponsor Medical Monitor.

- After randomization and start of study drug, an IOP of ≥ 21 mmHg AND an increase > 10 mmHg from the Visit 2 (POD1)/pre-dose baseline (both criteria must be met) is considered clinically significant and the Investigator should consider starting non-prostaglandin-based IOP-lowering medication while continuing the study drug, with appropriate follow-up at the next planned visit or at an unscheduled visit.
 - If the IOP reduction is satisfactory at the next visit, the subject may continue on study drug.
 - If the IOP reduction of IOP is not satisfactory at the next visit, then the study drug may be discontinued and alternative IOP-lowering medication may be started, after consultation with the Study Medical Monitor. The subject should continue in the study and complete the assessments indicated in Table 1 through Visit 6 (POD22) (Main Study) or Visit 7 (POD85) (Endothelial Cell Sub-study). The Study Medical Monitor should discuss the persistent elevation of IOP with the Sponsor Medical Monitor.

Medications used for treating increased IOP will be recorded in the Concomitant Medications section of the eCRF, noting that they were used to reduce IOP.

10.0 STATISTICAL CONSIDERATIONS

10.1 STATISTICAL ANALYTICAL PLAN

The Statistical Analysis Plan (SAP) will describe the details of all efficacy and safety analyses and will be finalized prior to database lock.

10.2 ANALYSIS POPULATIONS

The analysis populations are defined as follows:

- Intent-to-Treat (ITT) Population: All subjects who are randomized to study drug. Following the ITT principle, subjects will be analyzed according to the treatment they are assigned to at randomization.

- Per-protocol (PP) Population: All subjects in the ITT population who (i) received at least 1 dose of study drug, (ii) do not have major protocol deviations that would impact the evaluation of efficacy and (iii) have at least 80% overall dosing compliance.
- Safety Population: All randomized subjects who receive at least one dose of study drug.

10.3 STATISTICAL METHODS

10.3.1 General Approach

All analysis variables will be summarized descriptively by treatment group. Summary statistics for continuous measures will include mean, standard deviation, median, and range. Categorical measures will be summarized by the number and percent of subjects.

10.3.2 Analysis of Efficacy

All efficacy analyses and summaries will be based on assessments in the study eye for each subject.

Subjects who are rescued at any time prior to Visit 5 (POD15) will be considered as treatment failures for the primary efficacy endpoints and the relevant secondary efficacy endpoints. For subjects who discontinue from the study prior to Visit 5 (POD15), the last observation carried forward (LOCF) approach will be used to impute missing data.

For continuous secondary efficacy endpoints, the LOCF approach will also be used to impute the data at visits after subjects are rescued.

The ACC count will be graded as shown below:

Grade	0	1	2	3	4
ACC Count	0 cell	1-5 cells	6-15 cells	16-30 cells	> 30 cells

10.3.2.1 Analyses of Primary Efficacy Endpoints:

The primary efficacy analyses to compare APP13007 against placebo will be conducted on the ITT population using the Pearson Chi-square statistic. Fixed sequence testing will be employed to maintain the 2-sided alpha = 0.05. The primary analyses will first test the difference between treatments in the proportion of subjects with ACC count = 0 (Grade = 0) at POD8 (Visit 4) maintained through POD15 (Visit 5). If the test is statistically significant at the 2-sided alpha = 0.05 level in favor of APP13007, the difference between treatments in the proportion of

subjects with Ocular Pain grade = 0 at POD4 (Visit 3) maintained through POD15 (Visit 5) will be tested at the two-sided alpha = 0.05 level.

To confirm the robustness of primary analysis results, sensitivity analyses, including using observed data from all subjects, will be performed. The detailed sensitivity analyses will be described in the SAP.

10.3.2.2 Analyses of Secondary Efficacy Endpoints:

Mean change-from-baseline in ACC Grade, ocular Pain Grade, ACF Grade and visual acuity at PODs 4, 8 and 15 will be analyzed using an analysis of covariance (ANCOVA). The ANCOVA model will include treatment as a fixed effect and baseline as a covariate. The rest of secondary efficacy endpoints will be analyzed using the same method described for the primary efficacy endpoints.

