9.1.1.3 Deleterious Effects of the Study Drug

The investigator may stop the study drug and withdraw the subject if in their opinion the study drug is having a deleterious effect on the subject's health or wellbeing. The investigator should make an effort to follow up the subject until the deleterious effect is resolved.

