10.4 SAMPLE SIZE ESTIMATION

The assumption for the sample size determination was estimated using the Package Inserts of Durezol®, Lotemax® and Inveltys® and results from the APP13007 Phase 2 study (CPN-201). The sample size for ACC count primary efficacy endpoint is based on the assumption of 26% of subjects in the APP13007 group with ACC Count = 0 at POD8 and maintained through POD15 and 12% of subjects in the matching vehicle placebo group. The two-group chi-square test, with a two-sided significance level of 5% and 92% power, requires 175 subjects per treatment group to detect the difference between APP13007 and placebo.

The same sample size using the assumption of 57% of subjects with Ocular Pain Grade = 0 at POD4 and maintained through POD15 in APP13007 group and 38% of subjects in placebo group will provide 95% power to detect the treatment difference.

With an estimated 5% dropout rate, this study will randomize approximately 185 subjects per treatment group for a total of approximately 370 subjects.

In the Endothelial Cell Sub-study, a sample size of 80 subjects per treatment group is considered adequate to evaluate the corneal endothelial cell parameters between treatment groups. With a 10% dropout rate, the Sub-study will enroll approximately 88 subjects per treatment group for a total of approximately 176 subjects to be randomized for the Endothelial Cell Sub-study.

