6.4.3 Handling Dropouts or Missing Data

6.4.3.1 Imputation of Missing Efficacy Data

The missing data handling rule for the study eye will be applied for the efficacy endpoints.

Missing data from subjects who discontinue the study before POD15 assessments without taking rescue medication:

For subjects who prematurely discontinue the study without taking rescue medication, the LOCF approach will be used to impute the missing data. The last observation will be the last assessment value after the first dose of study drug and up to two days following the last dose of study drug.

Missing data from subjects who discontinue the study before POD15 assessments and take rescue medication before POD15 assessments:

For both categorical and continuous secondary efficacy endpoints of ACC grade, ocular pain grade and ACF grade, subjects who take rescue medication before POD15 assessments and prematurely discontinue the study, the LOCF approach will be used to impute the missing data. The last observation will be the last assessment value after the first dose of study drug and prior to starting rescue medication.

Intermittent missing data:

The likelihood of having intermittent missing data is low. For subjects with intermittent missing data for efficacy endpoints, the LOCF approach will be applied to impute the missing data, i.e., using the data collected from the most recent prior visit after the first dose of study drug.

If no data can be carried forward (i.e., missing assessments at POD 4 visit or no available post-baseline assessments), missing data will be treated as missing for the continuous endpoints and will be considered as 'Non-responder' for the categorical endpoints.

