10.1.3 Sensitivity Analyses

Sensitivity analyses will be performed to confirm the robustness of the primary efficacy analysis results:

1. Analysis of the primary endpoints will be performed using the PP population.
2. “Completed-Case” analysis of the primary endpoints will be performed using the subgroup of Completers based on the ITT population. Completers are defined as the subjects who complete the study and have the data for the ACC count and ocular pain grade assessments at all visits up to POD15.
3. “Observed-Case” analysis of the primary endpoints will be performed using the ITT population and the observed data for subjects who miss one of the assessments used to determine the primary endpoints without taking rescue medication. The subjects with missing data will be considered as treatment failures (Non-responders).
4. “Worst-Case in the Analysis Window” analysis of the primary endpoints will be performed using the ITT population and using the worst Response at PODs 4, 8 and 15 when multiple efficacy assessments fall within the same analysis window for each Analysis Visit.
5. If more than 5% of data are missing for determining the primary efficacy endpoints in any treatment group, a tipping point analysis will be performed when the statistical significance of a treatment difference between two groups has been claimed for each of the two primary

endpoints. Missing data for subjects who take a rescue medication will not be considered as 'missing' since the subjects will have been assigned as treatment failures (Non-responders).

The tipping point analysis of the primary endpoints will be performed using the ITT population to determine the number of subjects with imputed data in the placebo group whose response status has to be changed from Non-Responder to Responder in order to make the treatment difference between the two treatment groups no longer statistically significant.

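### LOCF as the primary rule lets a non-rescued dropout count as a sustained responder without examination at the visits that define the endpoint

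*Protocol*

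**What the plan says.** Protocol 10.3.2 sets the rule for the efficacy analyses: "For subjects who discontinue from the study prior to Visit 5 (POD15), the last observation carried forward (LOCF) approach will be used". SAP 6.4.3.1 restricts it to subjects without rescue: "For subjects who prematurely discontinue the study without taking rescue medication, the LOCF approach will be used to impute the missing data". Other parts of the SAP fix what this means in practice:

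- **Value carried (6.4.3.1).** Any assessment after the first dose and up to two days after the last dose qualifies. It need not come from a visit that defines the endpoint. Intermittent gaps are also filled by LOCF. With nothing to carry, a categorical endpoint is scored Non-responder.
- **Rescue (6.4.2).** Rescue before the POD15 assessments is failure.
- **Primary table (10.1.2).** Responders are split into those with and without imputed data. Both count as response.
- **Sensitivity analyses (10.1.3).** These include a completers analysis and an Observed-Case analysis, in which "The subjects with missing data will be considered as treatment failures (Non-responders"). A tipping point is conditional on more than 5% missing in an arm and on significance having been claimed.
- **Discarded data (6.3.5).** If dosing lasted under 14 days, assessments more than two days after the last dose are not used.

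LOCF applies whatever the reason for leaving. Protocol 9.1.1.3 gives one such reason: "The investigator may stop the study drug and withdraw the subject if in their opinion the study drug is having a deleterious effect" on the subject. Protocol 6.3 adds that a subject who asks to stop study drug is withdrawn from the study.

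**The concern.** The endpoints are worded as outcomes held over time, and the primary analysis can supply that holding by assumption. For ACC, the gatekeeping endpoint, a single clear examination at POD4 can stand in for both POD8 and POD15. For pain, POD4 must be observed, but everything after it can be imputed. A subject withdrawn because the drug was judged harmful is credited as a success if the last grade was 0.

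At stake is whether the primary proportion means what the endpoint says, and whether a close ACC result could rest on imputed responders. Testing is in fixed sequence, so a lost ACC result also ends formal testing of pain.

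**Working it through.** **Inputs.** The test is "conducted on the ITT population using the Pearson Chi-square statistic" (protocol 10.3.2). Protocol 10.4 gives the ACC rates, "26% of subjects in the APP13007 group with ACC Count = 0 at POD8 and maintained through POD15 and 12% of subjects" on placebo, and the pain rates, "57% of subjects with Ocular Pain Grade = 0 at POD4 and maintained through POD15 in APP13007 group and 38% of subjects" on placebo. It also gives the design statement "with a two-sided significance level of 5% and 92% power, requires 175 subjects per treatment group", a stated 95% power for pain, 5% dropout and 185 randomized per arm.

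**Reproducing the plan.** With Δ = p1 − p2 and p̄ the mean rate, power = Φ{[Δ − 1.96√(2p̄(1−p̄)/n)] / √[(p1(1−p1) + p2(1−p2))/n]}.

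- ACC, n = 175: (0.14 − 0.0822)/0.0413 = 1.40, power 91.9% (stated 92%).
- Pain, n = 175: (0.19 − 0.1046)/0.0524 = 1.63, power 94.8% (stated 95%).
- Dropout: 175/0.95 = 184.2, rounded up to 185.

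**Direction of the credit.** Compare the event that LOCF scores as response with the event under full observation.

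| Last usable visit | Scored as response under LOCF | Response if fully observed | Relation |
|---|---|---|---|
| Pain, POD4 | 0 at POD4 | 0 at POD4, 8 and 15 | LOCF at least as generous |
| Pain, POD8 | 0 at POD4 and 8 | 0 at POD4, 8 and 15 | LOCF at least as generous |
| ACC, POD8 | 0 at POD8 | 0 at POD8 and 15 | LOCF at least as generous |
| ACC, POD4 | 0 at POD4 | 0 at POD8 and 15 | Neither contains the other |

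In the last row, a subject with cells at POD4 who would have cleared by POD8 is scored Non-responder. The bias can therefore run either way.

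**Effect at the planned result.** 5% of 185 is 9.25, so about 9 subjects per arm. For equal arms, X² = 370(a − b)² / [(a + b)(370 − a − b)]. The recoded rows suppose that nine APP13007 responders were imputed and no placebo responder was.

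| Responders of 185 (APP13007 vs placebo) | X² | p |
|---|---|---|
| ACC as planned, 48 vs 22 | 11.91 | 0.0006 |
| ACC, nine recoded, 39 vs 22 | 5.67 | 0.017 |
| Pain as planned, 105 vs 70 | 13.28 | 0.0003 |
| Pain, nine recoded, 96 vs 70 | 7.39 | 0.007 |

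**Effect at the edge.** ACC 37 vs 22 gives p = 0.033, 36 vs 22 gives 0.045, and 35 vs 22 gives 0.061. Pain 89 vs 70 gives 0.046, and 88 vs 70 gives 0.059.

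**False-positive rate (assumed imputed rates; the documents give none).** Take a true ACC rate of 12% in both arms, 5% missing, and arm rate = 0.95 × 0.12 + 0.05q, where q is the imputed response rate. Exact binomial enumeration gives the chance of significance in favour of APP13007:

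- equal q in both arms (0 or 12%): 2.5–2.6%;
- q = 25% active and 0% placebo: 5.7%;
- q = 50% active and 0% placebo: 11.0%.

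**Tipping-point trigger.** 9/185 = 4.9% does not exceed 5%; 10/185 = 5.4% does.

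**Power with missing scored Non-responder, n = 185.** Rates are multiplied by (1 − d), where d is the missing fraction.

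| d | ACC rates | ACC power | Pain rates | Pain power |
|---|---|---|---|---|
| 5% (planned) | 24.7% vs 11.4% | 91.7% | 54.2% vs 36.1% | 94.0% |
| 10% (assumed) | 23.4% vs 10.8% | 89.9% | 51.3% vs 34.2% | 91.7% |

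**The case against.** The strongest reply is that the plan already shows the reader what is needed. Imputed responders appear on their own line, Observed-Case is exactly the alternative rule, and a completers analysis is added. Rescue as failure, nothing to carry as Non-responder, and LOCF otherwise form a coherent order. A sensitivity analysis is meant to differ from the primary. Withdrawn subjects should also have the Visit 6 assessments at termination (protocol 6.2.10). That examination may be recent enough to carry, or may fall in the Study Day 7–11 or 12–17 window and count as observed.

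Most of this stands. It reduces the point to which rule is primary. It does not remove it, because the plan gives no rule for an Observed-Case result that disagrees with the primary. Nor does the tipping point fill the gap: it may not run at the planned dropout, it runs only after significance, and in the SAP it changes only placebo Non-responders, never imputed APP13007 responders. Protocol 10.6 describes it without that one-arm limit.

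It is also fair to say that the alternative is not neutral. If placebo loses more subjects, scoring missing as Non-responder lowers placebo more and favours APP13007.

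A reader might take the FDA's agreement with the endpoints (protocol 3.3.2) as support for the missing-data rule. The documents record agreement with the endpoints. The SAP's change summary mentions FDA comments on LOCF only for the secondary endpoints.

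**Conclusion.** The point holds as one about the choice of primary rule. Following the plan as written, a non-rescued subject can be a primary responder with the defining visits unexamined: both visits for ACC, and POD8 and POD15 for pain. At the planned effect and 5% dropout the conclusions survive even the one-sided recoding of nine subjects. The rule matters for a borderline result or for imputed response that differs between arms, where one or two subjects can decide ACC and with it access to the pain test.

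Stronger readings that the documents do not support:

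- **That LOCF always inflates response, or that dropouts respond at least as often as completers.** This fails for ACC values carried from POD4.
- **That a dropout ending at 0 is the only unobserved outcome credited.** Intermittent gaps are filled the same way.
- **That a minimum number of imputed responders can be read from the 5% dropout**, for example 9 × 0.57 = 5.1 and 9 × 0.38 = 3.4 for pain. Protocol 10.4 does not say when dropout occurs, and follow-up runs past POD15. Subjects with nothing to carry are Non-responders.
- **That the difference is inflated by 9/185 = 4.9 points.** This needs every APP13007 dropout to end at 0 and no placebo dropout at all.

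**What to change.** Before unmasking, amend protocol 10.3.2 and SAP 6.4.3.1 and 10.1.2 as follows.

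1. Make the rule in SAP 10.1.3 item 3 primary. Score as Non-responder any non-rescued subject without an assessment in the analysis window of a defining visit: POD8 and POD15 for ACC; POD4, POD8 and POD15 for pain. Keep LOCF as a sensitivity analysis in its place.
2. If LOCF must stay primary, at the least do not carry a pre-POD8 value into the ACC endpoint, and score withdrawal for an adverse event or lack of efficacy as Non-responder.
3. State how the rule works with SAP 6.3.5. A subject dosed under 14 days and examined at POD15 more than two days after the last dose currently has that examination discarded. The SAP should say whether such a subject counts as missing.
4. Run the tipping point whatever the missing rate, and vary imputed outcomes in both arms.

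The cost is wording and programming; data collection and sample size do not change. Responder rates fall slightly in both arms. At 5% missing, power stays within about one point of the stated values; at an assumed 10% it is about two points lower for ACC and three for pain. The risk of favouring APP13007 when placebo loses more subjects remains, and the two-arm tipping point would show it.
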